3.3.2 Management of Hepatitis

3.3.2.1 Management of Hepatitis reactivation

In cancer patients with hepatitis B, whether carriers or in chronic state, use of antivirals during anticancer therapy has been shown to reduce the risk of hepatitis B virus (HBV) reactivation and associated HBV morbidity and mortality (Loomba et al. 2008).

3.3.2.1.1 Monitoring and prophylactic treatment for hepatitis B reactivation

Table 3-3 provides details of monitoring and prophylactic therapy according to the baseline results of viral load and serologic markers testing.

Table 3-3: Action to be taken for positive baseline hepatitis B results

Test	Result	Result	Result	Result	Result
HBV-DNA	+	+ or -	-	-	-
HBsAg	+ or -	+	-	-	-
HBs Ab	+ or -	+ or -	+ and no prior HBV vaccination	+ or -	- or + with prior HBV vaccination
HBc Ab	+ or -	+ or -	+ or -	+	-
Recommendation	Prophylaxis treatment should be started 1-2 weeks prior to first dose of study drug Monitor HBV-DNA approximately every 4 weeks		No prophylaxis Monitor HBV-DNA approximately every 4 weeks		No specific action

Antiviral prophylaxis therapy should continue for at least 4 weeks after last dose of study drug. For hepatitis B reactivation, definition and management guidelines, see Table 3-4 Guidelines for management of hepatitis B.

Table 3-4: Guidelines for management of hepatitis B

HBV reactivation (with or without clinical signs and symptoms)*	

For patients with baseline results: Positive HBV-DNA OR positive HBsAg ----- reactivation is defined as: [Increase of 1 log in HBV-DNA relative to baseline HBV-DNA value OR new appearance of measurable HBV-DNA] AND ALT elevation x 5 ULN
	
Treat: Start a second antiviral AND Interrupt study drug administration until resolution: ≤ grade 1 ALT (or baseline ALT, if > grade 1) and ≤ baseline HBV-DNA levels If resolution occurs within ≤ 28 days study drug should be re-started at one dose lower, if available. If the patient is already receiving the lowest dose of study drug according to the protocol, the patient should restart at the same dose after resolution. Both antiviral therapies should continue at least 4 weeks after last dose of study drug. If resolution occurs > 28 days Patients should discontinue study drug but continue both antiviral therapies at least 4 weeks after last dose of study drug.


For patients with baseline results: Negative HBV-DNA and HBsAg AND [Positive HBs Ab (with no prior history of vaccination against HBV), OR positive HBc Ab] ----- reactivation is defined as: New appearance of measurable HBV-DNA
	
Treat: Start first antiviral medication AND Interrupt study drug administration until resolution: ≤ baseline HBV-DNA levels If resolution occurs within ≤ 28 days study drug should be re-started at one dose lower, if available. If the patient is already receiving the lowest dose of study drug according to the protocol, the patient should restart at the same dose after resolution. Antiviral therapy should continue at least 4 weeks after last dose of study drug. If resolution occurs > 28 days Patients should discontinue study drug but continue antiviral therapy at least 4 weeks after last dose of study drug.

* All reactivations of hepatitis B are to be recorded as grade 3 (CTCAE v 4.0 Metabolic Laboratory/Other: Viral Re-activation), unless considered life threatening by the investigator; in which case, they should be recorded as grade 4 (CTCAE v 4.0 Metabolic Laboratory/Other: Viral Re-activation). Date of viral reactivation is the date on which **both** DNA and ALT criteria were met (e.g. for a patient who was HBV-DNA positive on 01-JAN-10 and whose ALT reached $\geq 5 \times$ ULN on 01-APR-10, the date of viral reactivation is 01-APR-10).

3.3.2.2 Monitoring for hepatitis C

The following two categories of patients should be monitored every 4 weeks for HCV reactivation:

- Patients with detectable HCV RNA-PCR test at baseline.
- Patients known to have a history of HCV infection, despite a negative viral load test at baseline (including those that were treated and are considered ‘cured’)

For definition of hepatitis C reactivation and the management guidelines, see Table 3-5 Guidelines for management of hepatitis C.

Table 3-5: Guidelines for management of hepatitis C

HCV reactivation*	
For patients with baseline results: Detectable HCV-RNA, reactivation is defined as: ALT elevation x 5 ULN	Discontinue study drug
For patients with baseline results: Knowledge of past hepatitis C infection with no detectable HCV-RNA, reactivation is defined as: New appearance of detectable HCV-RNA	Discontinue study drug

* All reactivations of hepatitis C are to be recorded as grade 3 (CTCAE v4.0 Metabolic Laboratory/Other: Viral Re-activation), unless considered life threatening by the investigator; in which case, they should be recorded as grade 4 (CTCAE v 4.0 Metabolic Laboratory/Other: Viral Re-activation).

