3.6.1.2 Brain MRI/CT

3.6.1.2.1 A brain MRI/CT will be done monthly x 2 then every other month, within 7 days of new cycle.

OR

3.6.1.2.2 For Phase II patients enrolled to the bevacizumab failure cohort, MRI/CT will be done every 4 weeks x 4, then every 8 weeks thereafter, within 7 days of new cycle.

Note: *MRI is the preferable imaging method, CT scan may be used in cases where an MRI cannot be obtained.

3.6.1.3 All relevant information regarding drug doses, concomitant medications, and doses, measurable lesions with measurements, tumor response, laboratory examinations, and treatment-related toxicities shall be documented in the patient's medical record and flow sheets.

3.6.1.4 A complete physical exam (with vital signs) and neurologic exam (to include documentation of the patients Karnofsky Performance Status) will be performed monthly. The MDASI-BT will be completed at baseline and at the time of each evaluation that includes an imaging study.

3.6.1.5 The patient will complete the MDASI-BT (Appendix 13.4) at the time of clinical evaluation with MRI as long as the clinical therapy is being administered, unless clinical deterioration makes self-report not possible before that time. The time when patients are unable to complete the self-report questionnaires will be used as part of the study analysis. The MDASI-BT will be completed only by the patient, unless changes in vision or weakness make this difficult. If this occurs, then the caregiver or research

assistant may read the questions to the patient or assist with marking the severity number or score as described by the patient. A patient caregiver may complete the questionnaires as a patient-preference proxy if the patient's deficits preclude self-report.

- 3.6.1.6 Patients on antiviral prophylaxis treatment or positive HBV antibodies should be tested for HBV-DNA on Cycle 1 Day 1 and Day 1 of all subsequent cycles (every 28 days) to monitor for re-activation. If re-activation is confirmed, everolimus must be interrupted or discontinued according to the guidance in Table 6-3. Patients with positive HCV RNA-PCR results at screening and/or a history of past infection (even if treated and considered 'cured') should have HCV RNA-PCR testing performed on Cycle 1 Day 1 and Day 1 of all subsequent cycles (every 28 days) to monitor for reactivation. Everolimus must be discontinued if HCV reactivation is confirmed according to the guidance in Table 3-5.

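### ALT is the sole trigger for stopping drug in HCV-RNA-positive patients and half of the HBV definition, but the screening and on-study chemistry lists name only SGOT

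*Combined protocol and SAP*

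**What the plan says.** Section 3.3.2.2 states: "The following two categories of patients should be monitored every 4 weeks for HCV reactivation". One category is patients with detectable HCV-RNA at baseline. For them Table 3-5 gives a single criterion, "Detectable HCV-RNA, reactivation is defined as: ALT elevation x 5 ULN", and a single action, discontinuation of study drug.

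For patients who are HBV-DNA or HBsAg positive at baseline, the first row of Table 3-4 requires a change in HBV-DNA "AND ALT elevation x 5 ULN". Drug is then interrupted until ALT returns to grade 1 or less (or to its baseline value, if that was above grade 1) and HBV-DNA is back to baseline or below. The footnote dates the event to the day on which both "DNA and ALT criteria were met".

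The liver tests actually listed are SGOT and bilirubin. This is so in the eligibility limits (2.1.1.6), the screening tests (2.2), the repeat baseline tests (2.5), the study calendar (3.5) and the four-weekly on-study chemistry (3.6.1.1). For hepatitis monitoring, 3.6.1.6 says that patients on antiviral prophylaxis or with HBV antibodies "should be tested for HBV-DNA on Cycle 1 Day 1 and Day 1 of all subsequent cycles", and it schedules HCV RNA-PCR at the same visits for patients with a positive HCV result or a history of infection. Footnote X9 of the calendar repeats this. Neither mentions ALT.

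**The concern.** A stopping rule works only if the quantity it depends on is measured. For HCV-RNA-positive patients the schedule orders a test that is not part of their definition and omits the one that is. Staff working from the calendar and 3.6.1.6 could comply in full and hold no ALT value to compare with five times the upper limit of normal. What is at stake is the safety of a small group of virus-positive patients taking an immunosuppressive drug: a mandatory discontinuation that is not triggered (HCV), or a reactivation recognised late (HBV).

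**Working it through.** No sample-size or power calculation applies. The check sets each definition beside the tests scheduled for it.

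| Baseline status | Criteria in the definition | Criteria on the schedule |
|---|---|---|
| HCV-RNA detectable (Table 3-5) | ALT | 0 of 1 |
| HBV-DNA or HBsAg positive (Table 3-4) | HBV-DNA and ALT | 1 of 2 (HBV-DNA) |
| HBV-DNA and HBsAg negative, antibody positive (Table 3-4) | HBV-DNA | 1 of 1 |
| Past HCV, no detectable RNA (Table 3-5) | HCV-RNA | 1 of 1 |

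**Scope.** Two of the four definitions need ALT; the other two use viral load alone and are fully scheduled.

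**Laboratory lists.** All five places that list liver tests name SGOT and none names ALT. They are not five separate gaps. Section 2.1.1.6 is an eligibility threshold, 2.5 is a conditional repeat of the screening tests, and 3.5 and 3.6.1.1 state the same on-treatment requirement. In substance ALT is missing once before treatment and once during it.

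**SGOT as a substitute.** SGOT is AST, and the protocol treats the two enzymes as distinct. The footnote to Table 3-9 names ALT and AST side by side, and 10.2.12.8 lists elevations of both among everolimus laboratory abnormalities. Neither reactivation table accepts SGOT.

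**HCV-RNA-positive patients.** RNA-PCR is run every cycle, but no RNA result can meet this group's criterion. An ALT rise accompanied by a similar SGOT rise would probably be noticed. An isolated ALT rise would not, unless the site happened to measure ALT.

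**HBV-DNA- or HBsAg-positive patients.** HBV-DNA each cycle supplies half of the definition and can prompt an ALT. The event remains assessable, but its recognition, its date and the restart decision depend on an unscheduled test. A missing baseline ALT removes only the allowance for a baseline above grade 1; the stricter default of grade 1 or less still applies.

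**Who is affected.** Section 2.1.4.9 excludes chronic or acute hepatitis B or C, 2.1.4.6 excludes chronic hepatitis again, and 2.2 lists HBV-DNA and HCV RNA-PCR among the pre-study tests. Yet 2.2, 3.3.2.2 and 3.6.1.6 all provide for virus-positive patients on study. Section 2.4 marks every cohort except Group B as closed, and 9.4 says that subjects at non-NCI sites were off treatment at Amendment C. The documents give no count; it must be small.

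**The case against.** The strongest reply is that the operative text already calls for ALT. Section 3.3.2.2 requires four-weekly monitoring and points to Table 3-5, where ALT is stated, and 3.6.1.6 sends the site to the same table. Sites may also run a full liver panel by habit. Scheduled SGOT and bilirubin, and the at-least-weekly laboratory testing after a toxicity in 3.3, add protection. Finally, eligibility and screening should keep nearly all such patients out.

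Much of this stands. It confines the problem to an omission from the schedule, in few patients, with an isolated ALT rise as the main exposure. It does not close the gap: 3.6.1.6 turns the monitoring duty into viral-load tests only, and a mandatory stop should not rest on inference or local custom.

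Three stronger readings are tempting and are not supported:

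- **A delay of months in HBV detection.** The Table 3-4 footnote takes, as its example, the rule "for a patient who was HBV-DNA positive on 01-JAN-10 and whose ALT reached" five times ULN three months later, and concludes that "the date of viral reactivation is 01-APR-10". Those dates only illustrate how to date an event. Under the footnote no reactivation exists until both criteria are met, so the interval is not a detection delay.
- **The Table 3-9 footnote lets treatment continue on SGOT alone.** It applies only when ALT and AST are both below ten times ULN. Using it requires an ALT value, which could then be read against Table 3-5.
- **HBV reactivation cannot be assessed.** HBV-DNA is repeated every cycle, giving a fresh prompt for ALT each time.

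**Conclusion.** The point holds as a gap between two safety rules and the schedule meant to feed them. In HCV-RNA-positive patients none of the defining criteria is scheduled, so an isolated ALT rise could go undetected and the discontinuation rule would not be triggered. In patients who are HBV-DNA or HBsAg positive, one of two criteria is scheduled and the event could be recognised late.

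This assumes that sites order what 3.5, 3.6.1.1 and 3.6.1.6 list and nothing more, and that at least one virus-positive patient is treated despite 2.1.4.6 and 2.1.4.9. The documents establish neither; they do show that the protocol plans for such patients. The number affected is not given and is small. A reader should not infer any effect on the progression-free survival endpoints or the cohort sizes, since neither uses ALT. The change is worth making because it makes a stated safety rule workable at little cost.

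**What to change.** Add ALT (SGPT) to the screening and baseline chemistry in 2.2 and 2.5, and to the every-4-week chemistry in 3.5 and 3.6.1.1, on the draws already taken. At minimum, name ALT in 3.6.1.6 on Cycle 1 Day 1 before dosing (to serve as baseline) and on Day 1 of each later cycle, for the virus-positive patients defined there.

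The cost is one analyte per existing draw, with no extra visit or needle stick; under the minimum version it applies only to virus-positive patients. The downside is that isolated ALT rises will surface and need grading.

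As a separate clerical correction, 3.6.1.6 refers HBV reactivation to Table 6-3, which does not appear in the document; the pointer should be to Table 3-4.

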3.3.3 Management of stomatitis/oral mucositis/mouth ulcers

CTCAE v 4.0 grade 1-2 stomatitis/oral mucositis/mouth ulcers due to everolimus should lead to using local supportive care such as use of mouthwash (avoid those containing alcohol). The use of topical high potency steroids such as triamcinolone oral paste 0.1% (Kenalog in Orabase®) is allowed. Please refer to section 3.3.1.2 for dose modifications. Suggested guidelines for treatment of stomatitis/oral mucositis/mouth ulcers:

1. For mild toxicity (grade 1), use conservative measures such as non-alcoholic mouth wash or salt water (0.9%) mouth wash several times a day until resolution.
2. For more severe toxicity (grade 2 in which case patients have pain but are able to maintain adequate oral alimentation, or grade 3 in which case patients cannot maintain adequate oral alimentation), the suggested treatments are topical analgesic mouth treatments (e.g., local anesthetics such as benzocaine, butyl aminobenzoate, tetracaine hydrochloride, menthol, or phenol) with or without topical corticosteroids, such as triamcinolone oral paste 0.1% (Kenalog in Orabase®).

3. Agents containing hydrogen peroxide, iodine, and thyme derivatives may tend to worsen mouth ulcers. It is preferable to avoid these agents.
4. Antifungal agents must be avoided unless a fungal infection is diagnosed. In particular, systemic imidazole antifungal agents (ketoconazole, fluconazole, itraconazole, etc.) should be avoided in all patients due to their strong inhibition of everolimus and sorafenib metabolism, therefore leading to higher everolimus exposures. Therefore, topical antifungal agents are preferred if an infection is diagnosed. Similarly, antiviral agents such as acyclovir should be avoided unless a viral infection is diagnosed.

Note: Stomatitis/oral mucositis should be appropriately graded using the functional grading given on the NCI-CTCAE, version 4.0.

3.3.4 Management of hyperlipidemia

Everolimus causes hyperlipidemia. Treatment of hyperlipidemia should take into account the pre-treatment status and dietary habits. Blood tests to monitor hyperlipidemia must be taken in the fasting state. Grade 2 or higher hypercholesterolemia (>300 mg/dL or 7.75 mmol/L) or grade 2 or higher hypertriglyceridemia (>2.5 x upper normal limit) should be treated with a statin or appropriate lipid-lowering medication, in addition to diet. Patients should be monitored clinically and through serum biochemistry for the development of rhabdomyolysis and other adverse events as required in the product label/data sheets for HMG-CoA reductase inhibitors. Please refer to section 3.3.1.2 for dose modifications of everolimus.

Note: Concomitant therapy with fibrates and an HMG-CoA reductase inhibitor is associated with an increased risk of a rare but serious skeletal muscle toxicity manifested by rhabdomyolysis, markedly elevated creatine kinase (CPK) levels and myoglobinuria, acute renal failure and sometimes death. The risk versus benefit of using this therapy should be determined for individual patients based on their risk of cardiovascular complications of hyperlipidemia.

3.3.5 Management of hyperglycemia

Grade 3 hyperglycemia has been observed in patients receiving everolimus therapy. In many cases the affected patients had an abnormal should have their glucose levels monitored during everolimus therapy. Please refer to section 3.3.1.2 for dose modifications.

3.3.6 Management of non-infectious pneumonitis

Table 3-6: Management of Everolimus-induced Pneumonitis

Worst grade pneumonitis	Required investigations	Management of pneumonitis	everolimus dose adjustment
Grade 1	CT scan with lung windows	No specific therapy is required	Administer 100% of everolimus dose
Grade 2	CT scan with lung windows. Consider pulmonary function	Symptomatic only. Prescribe corticosteroids if	Reduce everolimus dose

Worst grade pneumonitis	Required investigations	Management of pneumonitis	everolimus dose adjustment
	testing including: spirometry, DLCO, and room air O2 saturation at rest. Repeat each subsequent Cycle until return to within normal limits. Consider a bronchoscopy.	cough is troublesome.	until recovery to \leq grade 1. Everolimus may also be interrupted if symptoms are troublesome. Patients will be withdrawn from the study if they fail to recover to \leq grade 1 within 3 weeks.
Grade 3	CT scan with lung windows and pulmonary function testing includes: spirometry, DLCO, and room air O2 saturation at rest; Repeat each subsequent Cycle until return to normal limits. Bronchoscopy is recommended.	Prescribe corticosteroids if infective origin is ruled out. Taper as medically indicated.	Hold treatment until recovery to \leq grade 1. May restart protocol treatment within 2 weeks at a reduced dose (by one level) if evidence of clinical benefit.
Grade 4	CT scan with lung windows and required pulmonary function testing includes: spirometry, DLCO, and room air O2 saturation at rest. Repeat each subsequent Cycle until return to baseline. Bronchoscopy is strongly recommended.	Prescribe corticosteroids if infective origin is ruled out. Taper as medically indicated.	Discontinue treatment.

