3.2 PHASE II STUDY DESIGN

3.2.1 Drug Administration

All patients treated on the phase II cohorts will receive a combination of sorafenib (7 days on, 7 days off) and everolimus daily over a 28-day cycle, as follows:

Sorafenib 400 mg BID PO (days 1-7 and days 15-21)

Everolimus 5 mg PO daily (days 1-28)

There is not a defined set of maximum number of cycles that a patient may have. Patients may continue with protocol therapy until criteria for “Off Treatment” is met. See Section **3.7.1**.

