3.3.1 Within Treatment Cycles

If a patient experiences toxicities during a treatment cycle, the treatment will be immediately suspended until a grade 1 or less toxicity. If the toxicity resolves to less than or equal to grade 1 within 2 weeks, the patient will be retreated at the dose level described in Table **3-2** below. (Refer to Table **3-6** and Table **3-7** for management of everolimus-induced toxicities and Table **3-8**, Table **3-9** and Table **3-10** for management of sorafenib-induced toxicities.) If toxicity persists, the patient should be taken off study.

Two dose reductions are permitted. Doses that are reduced for sorafenib or everolimus related toxicity will not be re-escalated, even if there is minimal or no toxicity with the reduced dose. Patients whose dose has been reduced for adverse events that are subsequently not felt to be related to sorafenib or everolimus may have the dose re-escalated after completion of one cycle with toxicities less than or equal to grade 1. If any patient has further toxicities that would require additional reductions, or if treatment is held for more than 2 consecutive weeks because of ongoing

toxicity, the Study PI will assess if the patient should remain in the study (if the patient has benefited from treatment).

Table 3-2: Dose Modification Table

DOSE LEVEL	SORAFENIB	EVEROLIMUS
1 (starting dose)	400 mg BID 7 days on 7 days off	5 mg daily
-1	400 mg AM dose 200 mg PM dose 7 days on 7 days off	5 mg daily
-2	200 mg AM dose 200 mg PM dose 7 days on 7 days off	5 mg daily

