3.3.7 Management of suspected everolimus toxicity

Table 3-7: Criteria for dose-modification in case of suspected everolimus toxicity and re-initiation of everolimus treatment

Toxicity	Actions

Non-hematological toxicity
 
Grade 2 (except pneumonitis – refer to Table 3-6)
 
Grade 3 (except hyperlipidemia*) (except pneumonitis – refer to Table 3-6)
 
Grade 4
	
If the toxicity is tolerable to the patient, maintain the same dose. If the toxicity is intolerable to patient, interrupt everolimus until recovery to grade ≤1. Then reintroduce everolimus at same dose. If event returns to grade 2, then interrupt everolimus until recovery to grade ≤1. Then reintroduce everolimus at same dose level.
 
Interrupt everolimus until recovery to grade ≤1. Then reintroduce everolimus at same dose level. For pneumonitis consider the use of a short course of corticosteroids.
 
Discontinue everolimus.

Hematological toxicity
 
Grade 2 Thrombocytopenia (platelets <75, ≥ 50x10⁹/L)
 
Grade 3 Thrombocytopenia (platelets <50, ≥ 25 x10⁹/L)
 
Grade 4 Thrombocytopenia (platelets < 25 x10⁹/L)
	
Interrupt everolimus until recovery to grade ≤1 (>75 x10⁹/L). Then reintroduce everolimus at initial dose. If thrombocytopenia again returns to grade 2, interrupt everolimus until recovery to grade ≤1. Then reintroduce everolimus at same dose level.
 
Interrupt everolimus until recovery to grade ≤1 (platelets ≥ 75 x10⁹/L). Then resume everolimus at same dose level. If grade 3 thrombocytopenia recurs, discontinue everolimus.
 
Discontinue everolimus.

Toxicity	Actions
Grade 3 Neutropenia (neutrophils $<1, \geq 0.5 \times 10^9/L$)	Interrupt everolimus until recovery to grade ≤ 1 (neutrophils $\geq 1.5 \times 10^9/L$). Then resume everolimus at the initial dose. If ANC again returns to Grade 3, hold everolimus until the ANC $\geq 1.5 \times 10^9/L$. Then resume everolimus dosing at same dose level. Discontinue patient from study therapy for a third episode of grade 3 neutropenia.
Grade 4 Neutropenia (neutrophils $< 0.5 \times 10^9/L$)	Interrupt everolimus until recovery to grade ≤ 1 (neutrophils $\geq 1.5 \times 10^9/L$). Then resume everolimus at the lower dose level. If grade 3 or grade 4 neutropenia occurs despite this dose reduction, discontinue everolimus.

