10.2.12.1 Non-infectious Pneumonitis

Non-infectious pneumonitis is a class effect of rapamycin derivatives, including everolimus. In the randomized study, non-infectious pneumonitis was reported in 14% of patients treated with everolimus. The incidence of CTCAE grade 3 and 4 non-infectious pneumonitis was 4% and 0%, respectively. Fatal outcomes have been observed.

Consider a diagnosis of non-infectious pneumonitis in patients presenting with non-specific respiratory signs and symptoms such as hypoxia, pleural effusion, cough, or dyspnea, and in whom infectious, neoplastic, and other causes have been excluded by means of appropriate investigations. Advise patients to report promptly any new or worsening respiratory symptoms.

Patients who develop radiological changes suggestive of non-infectious pneumonitis and have few or no symptoms may continue everolimus therapy without dose alteration. If symptoms are moderate, consider interrupting therapy until symptoms improve. The use of corticosteroids may be indicated. Everolimus may be reintroduced at 5 mg daily.

For cases where symptoms of non-infectious pneumonitis are severe, discontinue everolimus therapy and the use of corticosteroids may be indicated until clinical symptoms resolve. Therapy with everolimus may be re-initiated at a reduced dose of 5 mg daily depending on the individual clinical circumstances.

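### Phase II everolimus stays at 5 mg at every level of Table 3-2, so the rules that reduce everolimus for toxicity have no target or lower only sorafenib

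*Combined protocol and SAP*

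**What the plan says.** Section 3.2.1 fixes the phase II dose: "Everolimus 5 mg PO daily (days 1-28"), with sorafenib 400 mg twice daily on days 1-7 and 15-21. After toxicity, section 3.3.1 takes the re-treatment dose from Table 3-2 and adds: "Two dose reductions are permitted". At the bottom level, -2, sorafenib is "200 mg AM dose 200 mg PM dose 7 days on 7 days off". The everolimus column reads 5 mg daily at all three levels.

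Three rows written for everolimus toxicity call for less everolimus:

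- **Table 3-6, grade 2 pneumonitis:** "Reduce everolimus dose" until recovery to grade 1 or less. Interruption is optional if symptoms are troublesome. A patient who has not recovered within 3 weeks is withdrawn.
- **Table 3-6, grade 3 pneumonitis:** hold until grade 1 or less, then "May restart protocol treatment within 2 weeks at a reduced dose (by one level) if evidence of clinical benefit". This stands in the column for everolimus dosing.
- **Table 3-7, grade 4 neutropenia:** "Then resume everolimus at the lower dose level". Everolimus is stopped if grade 3 or 4 neutropenia occurs despite that reduction.

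Sections 3.3.1.1 and 3.3.1.2 also lower the suspect drug, whichever of the two it is. The step is one level after ANC below 750 or platelets below 50,000, one level after grade 3 non-hematologic toxicity, and two levels after grade 4.

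Table 3-4, for hepatitis B reactivation, is the one place that foresees a patient with nowhere lower to go: "If the patient is already receiving the lowest dose of study drug according to the protocol, the patient should restart at the same dose". The drug-information text in 10.2.12.1 says of severe pneumonitis: "Therapy with everolimus may be re-initiated at a reduced dose of 5 mg daily depending on the individual clinical circumstances".

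**The concern.** A dose-reduction rule works only if the dose table contains a lower dose of the drug in question. For phase II everolimus it does not. Table 3-6 concerns pneumonitis caused by everolimus, which 10.2.12.1 describes as a class effect in which fatal outcomes have been observed. A patient who meets the grade 3 restart conditions and is moved one level down resumes everolimus at the dose that preceded the event and gives up part of the sorafenib dose instead. At grade 2 the investigator is told to lower everolimus but not to what dose.

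The stake is patient safety and uniform handling of the drug suspected of causing the event. The primary analysis is not involved.

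**Working it through.** The plan states no figure to reproduce. The check sets each rule against the dose table and then sizes the exposed group.

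**Step 1. What one level down means (Table 3-2, dosing days).**

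| Level | Sorafenib, mg/day | Change from start | Everolimus, mg/day | Change from start |
|---|---|---|---|---|
| 1 | 400 + 400 = 800 | - | 5 | - |
| -1 | 400 + 200 = 600 | (800 - 600)/800 = 25% lower | 5 | 0% |
| -2 | 200 + 200 = 400 | (800 - 400)/800 = 50% lower | 5 | 0% |

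Table 3-1 (phase I) does not help, because its everolimus doses are 5, 7.5 and 10 mg. No everolimus dose below 5 mg is defined in either table.

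**Step 2. Each rule against that table.**

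- *Grade 2 pneumonitis* names everolimus and no level. There is no target dose.
- *Grade 3 pneumonitis* speaks of protocol treatment and one level. It can be followed through level -1, which gives sorafenib -25% and everolimus 0%.
- *Grade 4 neutropenia* can be followed only through level -1, with the same result. Its stopping condition, recurrence despite the reduction, then assumes an everolimus reduction that never took place.
- *3.3.1.1 and 3.3.1.2* ask for one or two levels lower of the suspect drug. If that is everolimus, both steps are 0%.

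Using level -1 for an everolimus toxicity also spends one of the two permitted reductions. Section 3.3.1 does not re-escalate doses reduced for drug-related toxicity, so sorafenib stays lower.

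**Step 3. Expected number of grade 3 pneumonitis cases.** Inputs:

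- Group B, the only open cohort (2.4): at most 32 patients.
- Grade 3 pneumonitis in the source trial (10.2.12.1): 4%.
- Median everolimus treatment in that trial (10.2.12.8): 141 days.
- Group B 3-month progression-free rates (7.2): 1% under the null, 12% under the alternative.

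Unscaled: 0.04 x 32 = 1.28.

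Scaling assumes exponential progression-free survival, treatment until progression, and risk proportional to time on treatment. With 3 months = 91.3 days, hazard = -ln(PFS3)/91.3, median = ln 2/hazard, and factor = median/141.

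| PFS3 | Hazard per day | Median days | Factor | Expected cases |
|---|---|---|---|---|
| 12% | 0.0232 | 29.8 | 0.212 | 1.28 x 0.212 = 0.27 |
| 1% | 0.0504 | 13.7 | 0.097 | 1.28 x 0.097 = 0.12 |

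Median is compared with median because the source trial's mean exposure is not given. At 0.27 expected cases, the chance of at least one is 1 - exp(-0.27) = 24%.

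**Step 4. Grade 2.** Pneumonitis of any grade was 14%, and grade 2 is not reported separately. If no source case were grade 1, grade 2-3 cases would be at most 0.14 x 32 = 4.48 unscaled, or 4.48 x 0.212 = 0.95 at the 12% alternative. The documents give no grade 4 neutropenia rate for everolimus, so that row is not sized.

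**The case against.** The best defense is that everolimus was deliberately fixed at 5 mg, the lowest phase I dose, and that the three rows are leftover wording. Most Table 3-7 rows say to resume at the same dose or to stop. Section 3.3 also covers phase I after cycle 1, where a step down from 7.5 or 10 mg was possible. This is plausible and bears on the choice of fix. It does not remove the contradiction, because those rows still apply to phase II.

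Safeguards exist. Dose questions go to the Study Chair or the coordinating center's research nurse (end of 3.3.9), and each patient is discussed every other week (6.7.1). Grade 2 allows interruption, and grade 4 pneumonitis requires discontinuation. Patients are therefore not left without a safety action, but none of these supplies the missing dose.

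A reader might infer more than the documents support:

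- *That the grade 3 and neutropenia rules cannot be carried out at all.* They can, through level -1. The fault is that this route spares everolimus.
- *That 10.2.12.1 orders a full-dose restart after severe pneumonitis.* It is permissive drug information, in a section that elsewhere takes 10 mg as the recommended dose. Tables 3-6 and 3-7 are the operative rules.
- *That a 2.5 mg step is required.* The tablet is listed in 10.2.5, but no phase I level tested that dose.
- *That many sites will improvise.* Section 9.4 says subjects at non-NCI sites were off treatment by Amendment C.

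**Conclusion.** The inconsistency is real and confined to the phase II safety rules. It is clearest at grade 2 pneumonitis, where the ordered reduction has no target. At grade 3 pneumonitis and grade 4 neutropenia the rule can be followed only in a form that lowers sorafenib by 25% and leaves everolimus at full dose. The suspect-drug rules in 3.3.1.1 and 3.3.1.2 have the same gap.

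Its size is small: about 0.1 to 0.3 grade 3 pneumonitis cases on like-for-like exposure scaling, and 1.3 without scaling. If pneumonitis tends to come early, the truth lies nearer the unscaled figure. Thirty-two patients is a ceiling, since the documents do not say how many had already been treated. The rate comes from single-agent everolimus in renal cancer, and the drug text is written around 10 mg, not 5 mg with sorafenib, so the figures are indicative only.

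Nothing here bears on alpha, power or the progression-free survival endpoints. The point should be corrected while Group B is open, because the event can be fatal and the correction is cheap.

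**What to change.** State in Table 3-2 that 5 mg daily is the lowest phase II everolimus dose and that everolimus is held or discontinued, not reduced. Then align the dependent rules:

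- **Table 3-6, grade 2:** hold everolimus until grade 1 or less, keeping the 3-week withdrawal limit.
- **Table 3-6, grade 3:** discontinue everolimus and state whether sorafenib may continue.
- **Table 3-7, grade 4 neutropenia, and everolimus-attributed events under 3.3.1.1 and 3.3.1.2:** state either same-dose restart or discontinuation, with the Table 3-4 fallback as the model.
- **10.2.12.1 (secondary):** add a note that Tables 3-6 and 3-7 govern and that 5 mg is the full phase II dose.

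As an optional alternative, the sponsor could define a 2.5 mg step. The amendment would then have to say whether it counts toward the two permitted reductions, and the sponsor would have to confirm supply and accept a dose not tested in phase I.

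The cost is a wording amendment, and the rare patient with grade 3 pneumonitis loses an everolimus restart that is now optional. If such a patient stopped before 2 weeks of both agents, 5.2.7 would make the patient inevaluable and replaced, which should be rare at these case numbers. Sample size and analysis do not change.
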